Data Analysis for Drug Repurposing for Effective Alzheimer's Medicines – Montelukast vs Fluticasone

NCT05457855

July 10, 2023

1. Comparison Details

a. Intended aim(s)

To evaluate the comparative risk of dementia onset between patients treated with Montelukast versus Fluticasone for asthma.

b. Primary endpoint

Incident dementia (i.e., Alzheimer's disease, vascular dementia, senile, presenile, or unspecified dementia, or dementia in other diseases classified elsewhere).

[figure not shown]
2. Person responsible for implementation

[figure not shown]
[name]

3. Data Source(s)

Medicare, 2008-2018

4. Study Design Diagrams

5. Cohort Identification

a. Cohort Summary

This study will employ a new user, active comparator, observational cohort study design comparing Montelukast versus Fluticasone. The patients will be required to have continuous enrollment during the baseline period of 365 days before initiation of study drugs (cohort entry/index date). Follow-up for the outcome (dementia) differs between analyses. Follow-up begins the day after drug initiation (analysis 1, 3, 4); 180 days after drug initiation (analysis 2).

b. Key details regarding cohort creation

Index date:

- Day of initiation of new Montelukast versus Fluticasone use

Inclusion criteria for analyses 1, 3, 4:

- Aged \geq 65 years on the index date
- 365 days enrollment in Medicare Parts A, B, and D with no HMO coverage
- No use of Montelukast versus Fluticasone, any time prior to index date (all available lookback approach with a minimum of 365 days)
- No diagnosis of dementia any time prior to and including index date
- No history of nursing home admission recorded in any time prior to and including index date
- At least two claims with asthma diagnosis recorded in 365 days prior to index date (ICD-9 493.0x, 493.1, 493.2x, 493.8x, 493.9x or ICD-10 J44.0, J44.1, J44.9, J45.2x, J45.3x, J45.4x, J45.5x, J45.9x)

Inclusion criteria for analysis 2:

- Aged \geq 65 years on the index date
- 365 days enrollment in Medicare Parts A, B, and D with no HMO coverage or 365 days registration with a practice contributing data to CPRD prior to index date
- No use of Montelukast versus Fluticasone, any time prior to index date (all available lookback approach with a minimum of 365 days)
- No diagnosis of dementia any time prior to and including index date
- No history of nursing home admission recorded in any time prior to and including index date

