- At least two claims with asthma diagnosis recorded in 365 days prior to index date (ICD-9 493.0x, 493.1, 493.2x, 493.8x, 493.9x or ICD-10 J44.0, J44.1, J44.9, J45.2x, J45.3x, J45.4x, J45.5x, J45.9x)

DREAM study protocol - Comparison 10 Montelukast vs Fluticasone

493.2x, 493.8x, 493.9x or ICD-10 J44.0, J44.1, J44.9, J45.2x, J45.3x, J45.4x, J45.5x, J45.9x)

- 180-day continuous use of Montelukast versus Fluticasone starting on the index date

c. Flowchart of the study cohort assembly

	Less Excluded Patients	Remaining Patients
All patients		23,466,175
Did not meet cohort entry criteria	-21,749,739	1,716,436
Excluded due to insufficient enrollment	-1,010,844	705,592
Excluded based on Dementia Exclusion	-113,159	592,433
Excluded based on Nursing Home Admission	-62,588	529,845
Excluded based on Peripheral artery disease		
Diagnosis	-454,167	75,678
Excluded anyone aged <65 at index	-24,145	51,533
Patients in Montelukast group		12,575
Patients in Fluticasone group		38,958
Final cohort		51,533

6. Variables

a. Exposure-related variables:

Study drug:

The study exposure of interest is initiation of Montelukast

Comparator:

Fluticasone

b. Covariates:

Demographics	
Age	Region
Gender	Calendar year of index date
Race	Low income subsidy

Dementia risk factors	
Diabetes	Depression
Obesity	Anxiety
Hypertension	Bipolar disorder
Coronary artery disease	Schizophrenia

Markers for healthy behavior, frailty, healthcare use	
Smoking	Number of outpatient visits
Mammography	Number of hospitalizations
Colonoscopy	Number of serum creatinine tests ordered
Fecal occult blood test	Composite frailty score
Influenza vaccination	Number of C-reactive protein tests ordered
Pneumococcal vaccination	Osteoporosis
Herpes zoster vaccination	Fractures
Bone mineral density test	Falls

DREAM study protocol - Comparison 10 Montelukast vs Fluticasone

Number of distinct generic agents	Use of supplemental oxygen
Number of emergency room visits	Combined comorbidity score

Other Asthma treatments and Asthma severity indicators	
Respiratory failure	LABA
Asthma exacerbation	SABA
Tuberculosis	SAMA
Lung Cancer	LAMA
Bronchiectasis	ICS (excluding Fluticasone)
Sarcoidosis	Omalizumab, Mepolizumab, Reslizumab, Benralizumab, Dupilumab
Pulmonary Hypertension	Leukotriene receptor antagonist (excluding Montelukast)
Interstitial lung disease, lung fibrosis, ARDS	Number of Pulmonologist visits
Acute Upper/ Lower Respiratory Tract infection	Pulmonary function test
Pneumonia	Antibiotics
Corticosteroids	

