Comedication use	
Lithium	Diuretics
Anti-epileptic mood stabilizers	Nitrates
Anti-epileptics (other than mood stabilizers)	Lipid lowering drugs
Atypical antipsychotics	Non-insulin diabetes medications
Benzodiazepines	Insulin
Serotonin-norepinephrine reuptake Inhibitors	Antidepressants
Selective serotonin reuptake inhibitors	Angiotensin II receptor blockers (ARBs)
Tricyclic antidepressants (TCAs)	Angiotensin converting enzyme inhibitors (ACEi)
Typical antipsychotics	Calcium channel blockers
Anticoagulants	Beta blockers
Antiplatelet agents	Disease-modifying antirheumatic drugs (DMARDs)

DREAM study protocol - Comparison 10 Montelukast vs Fluticasone

Comorbid conditions	
Atrial fibrillation	Ischemic heart disease
Coronary artery disease	Chronic obstructive pulmonary disease
Heart failure	Malignancy
Stroke or transient ischemic attack	Drug or alcohol abuse or dependence
Peripheral vascular disease	Venous thromboembolism
Hyperlipidemia	Chronic liver disease
Renal dysfunction	Rheumatoid Arthritis

ICD-9, ICD-10, HCPCS, and NDC codes used to define the covariates listed above are available in Appendix A.

c. Outcome variables and study follow-up:

- **Primary outcome:** incident dementia, i.e., Alzheimer's disease, vascular dementia, senile, presenile, or unspecified dementia, or dementia in other diseases classified elsewhere. Outcome will be defined by 1 inpatient claim or 2 outpatient claims in analysis 1, 2, 3. In analysis 4, the outcome will be defined by 1 inpatient or 1 outpatient claims and 1 prescription claim for a symptomatic treatment [donepezil, galantamine, rivastigmine, and memantine] within 6 months of each other with outcome date assigned to second event in the sequence.
- Secondary outcomes: Individual component:
Alzheimer's disease

Condition	ICD-9 and ICD-10 codes
Alzheimer's disease	331.0*, F00*, G30*
Vascular dementia	290.4*, F01*
Senile, presenile, or unspecified dementia	290.0*, 290.1*. 290.3*, 797*, F03*
Dementia in other diseases classified elsewhere	331.1*, 331.2*, 331.7*, 294.1*, F02*

For analysis 1,3, and 4 the follow-up will start the day after initiation of Montelukast and Fluticasone and will continue until the earliest date of the following events:

- The first occurrence of the outcome of interest
- The date of end of continuous registration in the database,
- End of the study period,

DREAM study protocol - Comparison 10 Montelukast vs Fluticasone

- Measured death event occurs,

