Bone mineral density test, n (%)	1743 (13.9)	5139 (13.2)	2.00	1743 (13.9)	1732 (13.8)	0.30
Number of distinct prescriptions, mean (SD)	12.3 (5.8)	12.5 (5.8)	-2.30	12.3 (5.8)	12.2 (5.7)	2.00
Number of emergency room visits, mean (SD)	0.7 (1.4)	0.8 (1.6)	-8.80	0.7 (1.4)	0.7 (1.2)	1.20
Number of outpatient visits, mean (SD)	12.5 (8.4)	12.4 (8.6)	1.10	12.5 (8.4)	12.5 (8.6)	0.90
Number of hospitalizations, mean (SD)	0.2 (0.6)	0.2 (0.6)	-6.60	0.2 (0.6)	0.2 (0.5)	1.40

DREAM study protocol - Comparison 10 Montelukast vs Fluticasone

Number of C-reactive protein tests ordered, mean (SD)	0.2 (0.8)	0.2 (0.9)	-1.20	0.2 (0.8)	0.2 (0.8)	0.40
Number of serum creatinine tests ordered, mean (SD)	0.9 (1.6)	1.1 (2)	#####	0.9 (1.6)	0.9 (1.5)	1.60
Composite frailty score, mean (SD)	0.2 (0.1)	0.2 (0.1)	#####	0.2 (0.1)	0.2 (0.1)	1.40
Osteoporosis, n (%)	1911 (15.2)	5814 (14.9)	0.80	1911 (15.2)	1912 (15.2)	0.00
Fractures, n (%)	877 (7)	2787 (7.2)	-0.70	877 (7)	893 (7.1)	-0.50
Falls, n (%)	641 (5.1)	2326 (6)	-3.80	641 (5.1)	656 (5.2)	-0.50
Use of supplemental oxygen, n (%)	260 (2.1)	1091 (2.8)	-4.80	260 (2.1)	279 (2.2)	-1.00
Combined comorbidity score, mean (SD)	2.2 (2.2)	2.4 (2.4)	#####	2.2 (2.2)	2.2 (2.2)	0.50
Comedication use, n (%)						
Lithium	17 (0.1)	50 (0.1)	0.20	17 (0.1)	12 (0.1)	1.20
Anti-epileptic mood stabilizers	142 (1.1)	562 (1.4)	-2.80	142 (1.1)	149 (1.2)	-0.50
Anti-epileptics (other than mood stabilizers)	1839 (14.6)	6087 (15.6)	-2.80	1837 (14.6)	1778 (14.1)	1.30
Atypical antipsychotics	170 (1.4)	719 (1.8)	-3.90	170 (1.4)	158 (1.3)	0.80
Benzodiazepines	2537 (20.2)	7878 (20.2)	-0.10	2537 (20.2)	2523 (20.1)	0.30
Serotonin-norepinephrine reuptake inhibitors	715 (5.7)	2343 (6)	-1.40	715 (5.7)	721 (5.7)	-0.20
Selective serotonin reuptake inhibitors	2265 (18)	7367 (18.9)	-2.30	2265 (18)	2205 (17.5)	1.20
Tricyclic antidepressants (TCAs)	434 (3.5)	1548 (4)	-2.80	434 (3.5)	425 (3.4)	0.40
Typical antipsychotics	20 (0.2)	105 (0.3)	-2.40	20 (0.2)	24 (0.2)	-0.80
Anticoagulants	1163 (9.2)	4342 (11.1)	-6.30	1163 (9.3)	1217 (9.7)	-1.50
Antiplatelet agents	947 (7.5)	3416 (8.8)	-4.50	947 (7.5)	916 (7.3)	0.90
Nitrates	915 (7.3)	3131 (8)	-2.90	915 (7.3)	881 (7)	1.10
Lipid lowering drugs	6790 (54)	22232 (57.1)	-6.20	6789 (54)	6819 (54.2)	-0.50
Non-insulin diabetes medications	2391 (19)	7537 (19.3)	-0.80	2388 (19)	2415 (19.2)	-0.50

DREAM study protocol - Comparison 10 Montelukast vs Fluticasone

Insulin	725 (5.8)	2740 (7)	-5.20	725 (5.8)	705 (5.6)	0.70

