Sarcoidosis, n (%)	60 (0.5)	259 (0.7)	-2.50	60 (0.5)	68 (0.5)	-0.90
Tuberculosis, n (%)	2157 (17.2)	7552 (19.4)	-5.80	2155 (17.1)	2177 (17.3)	-0.50
Acute Upper/ Lower Respiratory Tract infection, n (%)	4789 (38.1)	14315 (36.7)	2.80	4788 (38.1)	4850 (38.6)	-1.00
Pulmonary function test, n (%)	4989 (39.7)	13566 (34.8)	10.00	4988 (39.7)	4943 (39.3)	0.70
Number of Pulmonologist visits, mean (SD)	1.1 (2.4)	1 (2.5)	3.50	1.1 (2.4)	1.1 (2.5)	0.90
Antibiotics, n (%)	9638 (76.6)	29724 (76.3)	0.80	9636 (76.6)	9601 (76.4)	0.70
Corticosteroids, n (%)	6750 (53.7)	18540 (47.6)	12.20	6748 (53.7)	6551 (52.1)	3.10
ICS (excluding Fluticasone), n (%)	3647 (29)	8369 (21.5)	17.40	3644 (29)	3386 (26.9)	4.60
LAMA, n (%)	884 (7)	3315 (8.5)	-5.50	884 (7)	883 (7)	0.00
LABA, n (%)	2532 (20.1)	12953 (33.2)	#####	2532 (20.1)	2143 (17)	8.00
Leukotriene receptor antagonist (excluding Montelukast), n (%)	93 (0.7)	150 (0.4)	4.70	91 (0.7)	68 (0.5)	2.30
SABA, n (%)	6687 (53.2)	21764 (55.9)	-5.40	6684 (53.2)	6657 (53)	0.40
SAMA, n (%)	656 (5.2)	2193 (5.6)	-1.80	656 (5.2)	629 (5)	1.00

9. Statistical analysis plans

Incidence rates for the outcome will be estimated for the treatment and reference groups before and after PS matching. The competing risk of death could be of concern for the current set of analyses if mortality is frequent among patients included in the cohort and if differences in the risk of mortality between treatment and reference groups are substantial. In the PS-matched sample, we will use cause-specific hazard models⁷ to provide hazard ratios averaged over the entire follow-up period as well as interval specific hazard ratios (1, 2, and 3 years) for the association between the treatment of interest and risk of ADRD after considering all-cause mortality as a competing event. Pre-specified subgroup analyses will be conducted based on age, sex, and baseline cardiovascular disease.

10. References

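### Baseline dementia is screened by diagnosis alone: earlier fills of the four drugs that analysis 4 uses as outcome evidence are neither an exclusion nor a propensity-score covariate

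*Combined protocol and SAP*

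**What the plan says.** Section 5b gives two inclusion lists, one for analyses 1, 3 and 4 and one for analysis 2. Both handle baseline dementia with the same line: "No diagnosis of dementia any time prior to and including index date". Neither mentions dementia drugs. The flowchart in section 5c has one relevant row, "Excluded based on Dementia Exclusion", with no separate row for drug fills.

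Section 6c defines the outcome by claims alone in analyses 1 to 3 (one inpatient or two outpatient). For analysis 4, "the outcome will be defined by 1 inpatient or 1 outpatient claims and 1 prescription claim". The drug half and the time window are given as "1 prescription claim for a symptomatic treatment [donepezil, galantamine, rivastigmine, and memantine] within 6 months of each other", and the outcome is dated to the second of the two. The text does not say that both must follow the index date.

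The covariate lists in section 6b and the balance table in section 8 hold many psychotropic and cardiometabolic classes, such as "Atypical antipsychotics", but none of the four drugs. Appendix A was not among the pages available. The plan describes its scope as follows: "ICD-9, ICD-10, HCPCS, and NDC codes used to define the covariates listed above are available in Appendix A". That is a code list for covariates already named, not a source of further exclusions.

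**The concern.** The plan treats a fill of donepezil, galantamine, rivastigmine or memantine as a marker of dementia after index but ignores the same marker before index. The endpoint is incident dementia. Where an earlier fill does reflect dementia, the disease predates the study drug and cannot be an effect of it.

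Such patients might be expected to receive a code fairly soon, although the documents offer no evidence on timing. If they do, the hazard ratio most exposed is the first of the planned "interval specific hazard ratios (1, 2, and 3 years". Analyses 1, 3 and 4 also censor 90 days after the last supply ends. Where that shortens follow-up, early events carry more weight.

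**Working it through.** **1. Who can enter and be counted**

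- Analyses 1 to 3: a patient with an earlier fill and no dementia code meets every entry criterion and becomes a case once the claims rule is met. Starting follow-up at day 180 in analysis 2 delays the count but does not remove the patient.
- Analysis 4: a dementia diagnosis on or before index excludes the patient, so the diagnosis half must follow index. The drug half has no such limit. A fill before index and a first diagnosis after it, within 6 months of each other, meets the rule and is dated to the diagnosis. Even if both halves must follow index, a refill by an earlier user can supply the drug half.
- The analysis 4 sentence has two readings. If an inpatient claim alone qualifies, the point about the drug half applies only to the outpatient route.

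**2. Size**

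The plan has no figure to reproduce. From the documents: 12,572 patients per matched arm. Assumed: 0.5% with an earlier fill and no code, 45% of these coded in year 1, all of the coded patients having had dementia before index, 15 true events per 1000 person-years, a true HR of 0.80, and no censoring.

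Observed HR = (HR × T + c_M) / (T + c_F), where T is true events in the fluticasone arm and c_M and c_F are prevalent cases counted in the montelukast and fluticasone arms.

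- T = 12,572 × 0.015 = 188.6
- c = 12,572 × 0.005 × 0.45 = 28.3 in each arm
- Observed HR = (150.9 + 28.3) / (188.6 + 28.3) = 179.2 / 216.9 = 0.826

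| Change to the base case | T | c | Observed HR |
|---|---|---|---|
| Earlier fills 0.1% | 188.6 | 5.7 | 0.806 |
| Earlier fills 1% | 188.6 | 56.6 | 0.846 |
| 30% coded | 188.6 | 18.9 | 0.818 |
| 60% coded | 188.6 | 37.7 | 0.833 |
| 20 events per 1000 | 251.4 | 28.3 | 0.820 |
| 10 events per 1000 | 125.7 | 28.3 | 0.837 |
| Half of coded cases truly prevalent | 188.6 | 14.1 | 0.814 |
| Three years, 75% coded | 565.7 | 47.1 | 0.815 |
| Analysis 4, half of true events captured | 94.3 | 28.3 | 0.846 |
| Same, half of coded cases prevalent | 94.3 | 14.1 | 0.826 |

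Setting the three main inputs (fills, share coded, incidence) to their worst values together gives c = 12,572 × 0.01 × 0.60 = 75.4 and (100.6 + 75.4) / (125.7 + 75.4) = 0.875.

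**3. Against sampling error**

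With 150.9 and 188.6 events, SE(log HR) = √(1/150.9 + 1/188.6) = 0.11. The shift is ln(0.826 / 0.80) = 0.032, about 0.3 SE.

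**4. Under a true null**

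With equal c in both arms the observed HR stays at 1. Scaling the imbalance on the matched atypical antipsychotics row (170 montelukast, 158 fluticasone) gives c_F = 28.3 × 158/170 = 26.3, and (188.6 + 28.3) / (188.6 + 26.3) = 1.01.

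**The case against.** The diagnosis exclusion is stronger than it may look. It uses all available history. Data start in 2008 and index years in the balance table run from 2014 to 2018, so look-back can span several years for patients enrolled long enough. It states no two-claim requirement, so it reads as stricter than the outcome rule. The nursing-home exclusion helps as well. The residual group is people who filled one of these drugs yet have no dementia code in all that time. They may be few, some will not have dementia, and patients who have gone uncoded so far need not be coded soon. All of this stands, and it is why the low end of the range is negligible. It does not close the gap, because neither exclusion as written looks at fills.

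The flowchart's dementia step may already have used fills. That is possible, but the criterion does not say so. The row (113,159 of 705,592, or 16.0%) does not settle how well the screen works in the final 51,533, because most later exclusions came after it.

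Excluding earlier users also removes some people without dementia who are properly at risk. That is true. The criterion would, however, rest on pre-index information and apply alike to both arms.

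A reader might infer that the gap could manufacture a protective effect, especially from the unmatched table, where several dementia-related rows differ between arms. The documents do not support this. Hazard ratios are estimated in the matched sample, where mean age is 72.8 in both arms, depression is 16.1% against 16.0%, and the antipsychotic row moves a null HR only to 1.01. This reassurance is indirect, since the four drugs have no row of their own.

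**Conclusion.** The gap is in the text: baseline dementia is defined by diagnosis alone, and the four drugs are neither excluded nor adjusted for, although analysis 4 treats a fill as evidence of disease. The likely consequence is modest attenuation. A true HR of 0.80 reads about 0.83 in the mid-range case and 0.81 to 0.85 when inputs vary one at a time. Fill prevalence, coding share and incidence are all assumptions, so the documents cannot show that the effect is material. Nor do they support reading every earlier fill as dementia, or expecting a spurious difference between arms. The point rests on a clear inconsistency that is cheap to remove. How analysis 2 treats outcomes recorded between index and day 180 is a separate question and adds nothing here.

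**What to change.** 1. Add to both inclusion lists a criterion excluding anyone dispensed donepezil, galantamine, rivastigmine or memantine at any time up to and including the index date. If the flowchart's dementia step already used these fills, state that in the criterion instead.
2. State that both components of the analysis 4 outcome must fall after index.
3. Report the number excluded on this ground, by arm, in the flowchart. This replaces the assumed prevalence with a count.
4. Re-run the propensity score, matching and balance table.

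The data are in hand: entry already requires "365 days enrollment in Medicare Parts A, B, and D with no HMO coverage", and NDC codes are already used to define covariates. The work is one criterion, one clarifying sentence and a re-run. The price is a small loss of patients, about 12,572 × 0.005 = 63 per matched arm at the assumed 0.5%, some of whom do not have dementia.

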- The date of drug discontinuation, defined as the date of the last continuous treatment episode of the index drug (Montelukast and Fluticasone) plus a defined grace period (i.e., 90 days after the end of the last prescription's days' supply in main analyses).

For analysis 2, the follow-up will start 180 days after initiation of Montelukast and Fluticasone and will continue until the earliest date of the following events:

- The first occurrence of the outcome of interest, unless otherwise specified for selected outcomes,
- The date of end of continuous registration in the database,
- End of the study period,
- Measured death event occurs,
- Maximum allowed follow-up time (1095 days) reached

7. Propensity score analysis

We will use a propensity-score (PS)¹-based approach to account for measured confounding in this study. The PS will be calculated as the predicted probability of initiating the exposure of interest (i.e., the repurposing candidate) versus the reference drug conditional on baseline covariates using multivariable logistic regression constructed separately in each data source. On average, patients with similar PSs have similar distribution of potential confounders used to estimate the PS. Therefore, analyses conditioned on the PS provide effect estimates that are free from measured confounding. For all our analyses, initiators of each exposure of interest will be matched with initiators of the reference exposure based on their PS within each data source.² Pair matching will be conducted using a nearest-neighbor algorithm, which seeks to minimize the distance between propensity scores in each pair of treated and reference patients,³ and a caliper of 0.025 on the natural scale of the PS will be used to ensure similarity between the matched patients.⁴

We report multiple diagnostics for PS analysis in this protocol. First, the PS distributional overlap is provided between two groups before and after matching to ensure comparability of these groups.⁵ Next, balance in each individual covariate between two treatment groups is reported using standardized differences.⁶

8. Table for covariate balance

Variable	Unmatched			PS-Matched		
	Montelukast (N = 12,575)	Fluticasone (N = 38,958)	St. Diff	Montelukast (N = 12,572)	Fluticasone (N = 12,572)	St. Diff
Demographics						
Age, mean (SD)	72.8 (6.1)	73.3 (6.4)	-8.20	72.8 (6.1)	72.8 (6.1)	-0.30
Gender, n (%)						
Male	3694 (29.4)	12706 (32.6)	-7.00	3694 (29.4)	3764 (29.9)	-1.20

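### The dementia code table counts ICD-9 797 (senility) as a primary event and does not pair 797, 331.1 and 331.2 fully with ICD-10, so the endpoint is built differently before and after the coding switch

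*Combined protocol and SAP*

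**What the plan says.** Section 1b gives the endpoint as "Incident dementia (i.e., Alzheimer's disease, vascular dementia, senile, presenile, or unspecified dementia, or dementia in other diseases classified elsewhere". Neither senility nor frailty is named there.

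Section 6c turns this into codes, with a wildcard after each:

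- Alzheimer's disease: ICD-9 331.0; ICD-10 F00 and G30.
- Vascular dementia: ICD-9 290.4; ICD-10 F01.
- Senile, presenile or unspecified dementia: "290.0*, 290.1*. 290.3*, 797*, F03".
- Dementia in other diseases: "331.1*, 331.2*, 331.7*, 294.1*, F02".

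The counting rule is "Outcome will be defined by 1 inpatient claim or 2 outpatient claims in analysis 1, 2, 3". Analysis 4 instead needs a diagnosis claim plus "1 prescription claim for a symptomatic treatment [donepezil, galantamine, rivastigmine, and memantine] within 6 months of each other".

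The data source in section 3 is "Medicare, 2008-2018", and the index years in the section 8 balance table run from 2014 to 2018. At baseline, section 5b requires "No diagnosis of dementia any time prior to and including index date" but gives no codes for that exclusion. The plan contains no crosswalk between code versions, no reason for including 797, and no analysis by coding period.

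**The concern.** There are two separate faults in the table.

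**797 does not match the stated endpoint.** Taken as senility without a dementia diagnosis, it records old age and debility. In analyses 1-3 a single inpatient claim is enough, with no second claim and no dementia drug. The plan elsewhere treats frailty as a baseline covariate, through the composite frailty score. No R code is listed, so nothing in the ICD-10 part of the table corresponds to 797.

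**331.1 and 331.2 are only partly paired.** These are legitimately classed as dementia in the table. Their only ICD-10 match is F02. G31.0 and G31.1 are absent, and the only G code in the table is G30.

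The first fault adds false events in the ICD-9 period only. The second may lose true events in the ICD-10 period only. Either way, an incidence rate or hazard ratio that spans the switch mixes two constructions of the outcome. Section 9 plans both crude incidence rates and hazard ratios by year of follow-up (1, 2 and 3), and these are the results most exposed.

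**Working it through.** The plan states no event count, by code or in total, so there is no plan figure to reproduce. The steps below size the problem.

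**Assumptions not in the documents:** code meanings follow standard ICD usage; the switch is 1 October 2015; entry is uniform within each calendar year; data end on 31 December 2018.

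**1. Index dates in the ICD-9 period.** Matched counts from section 8, with 12,572 per arm:

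| Index year | Montelukast | Fluticasone |
|---|---|---|
| 2014 | 3142 | 3037 |
| 2015 | 2585 | 2519 |

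- Montelukast: (3142 + 0.75 × 2585)/12,572 = 40.4%.
- Fluticasone: (3037 + 0.75 × 2519)/12,572 = 39.2%.
- Pooled: (6179 + 0.75 × 5104)/25,144 = 39.8%.
- Standardized difference between arms, on the table's scale: 2.5. If 50% to 100% of 2015 entries precede the switch, the pooled share is 34.7% to 44.9% and the difference 2.3 to 2.7.

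**2. Follow-up in the ICD-9 period.** This is what determines outcome exposure. Time on treatment is taken as exponential for the on-treatment analyses. For analysis 2, follow-up runs from day 180 to the cap ("Maximum allowed follow-up time (1095 days) reached") with no other loss.

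| Scenario | Montelukast | Fluticasone |
|---|---|---|
| Mean 0.5 year on treatment | 33% | 32% |
| Mean 1 year | 27% | 26% |
| Mean 2 years | 21% | 21% |
| Analysis 2 | 10% | 10% |

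**3. ICD-9 share by year since initiation.** The earliest index date is January 2014, so ICD-9 follow-up cannot last beyond 21 months. With no dropout, the pooled share of person-time is about 32% in year 1, 9% in year 2 and 0% in year 3.

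**4. Dilution.** Let f be the share of reference-arm events that are false positives with no treatment effect. Then observed HR = HR × (1 − f) + f. Write f = w × p, where w is the share of events in the ICD-9 period (taken to follow person-time) and p is the false share among those. The true HR is set at 0.80 for illustration.

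- Within the ICD-9 period, p = 2% to 5%: 0.80 × 0.98 + 0.02 = 0.804; 0.80 × 0.95 + 0.05 = 0.81.
- Overall, w = 0.10 to 0.33 and p = 2% to 5%: f = 0.2% to 1.65%; HR = 0.8004 to 0.8033.
- Overall, wider range, w = 0.10 to 0.35 and p = 5% to 30%: f = 0.5% to 10.5%; HR = 0.801 to 0.821.
- By year, at the extreme p = 30%: year 1, f = 0.32 × 0.30 = 0.096, HR = 0.819; year 2, f = 0.09 × 0.30 = 0.027, HR = 0.805; year 3, HR = 0.80. A constant effect would appear to strengthen with time purely because of the code list.

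The number of events qualifying on 797 alone is unknown, so p is an assumption throughout.

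**The case against.** The strongest defence is that the effect on the main hazard ratio is small and falls equally on both arms. Calendar year is a propensity-score covariate, and every matched index-year difference is at most 1.90. Most follow-up is in the ICD-10 period. Analysis 4 cannot count a 797 claim without a dementia drug claim. All of this stands, and it limits the size of the point.

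A reader might infer four stronger things, which the documents do not support:

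- **That all three codes are non-dementia frailty codes.** Only 797 fits that description. The table classes 331.1 and 331.2 as dementia, and the complaint about them is pairing alone.
- **That the endpoint becomes a different one after the switch, so the same patient is a case before it and not after.** All four categories have ICD-10 codes, and F02 or F03 will capture some of the patients concerned. The Alzheimer's disease and vascular dementia rows are untouched, so the named secondary outcome is unaffected. What can be said is that equivalence is not shown, and that for 797 no listed code carries it forward.
- **That the entry criterion also changes at the switch.** This would follow only if the baseline exclusion uses the outcome list, and the plan does not say so.
- **That the false events track lung-disease severity and so bias the comparison.** This is a hypothesis. After matching, standardized differences are 1.40 for the frailty score and for hospitalizations, 0.60 for respiratory failure and 2.40 for asthma exacerbation.

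None of this answers the remaining point. Balance between arms does not stop the outcome construction from changing with time since initiation, and nothing in the plan justifies counting 797.

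**Conclusion.** The concern holds in this form. Followed as written, the table counts senility claims as primary dementia events in analyses 1-3, in one coding period only, and pairs 331.1 and 331.2 incompletely across versions. About 40% of matched index dates and roughly 20%-33% of on-treatment follow-up (about 10% in analysis 2) are exposed to the ICD-9 list.

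The likely overall effect is slight dilution toward the null, in the third decimal place for 2%-5% false events and up to about 0.02 on a hazard ratio of 0.80 under the widest assumptions. The step in crude incidence rates and the possible false trend across the interval-specific hazard ratios matter more for interpretation.

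These figures rest on standard code meanings, an October 2015 switch, uniform entry within year and an assumed false-positive share. Only the study team can replace that last assumption, by counting events. The change should be made because it concerns the primary outcome definition and is cheap to correct.

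**What to change.** - Remove 797 from the primary outcome list. Report, as a sensitivity analysis, the result with it included and the number of events in each arm that qualify on 797 alone.
- Add G31.0 to pair with 331.1, and G31.1 to pair with 331.2. Set out the table as matched ICD-9 and ICD-10 columns.
- State that this same paired list defines the baseline dementia exclusion, and re-run cohort assembly, matching and analyses.

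The cost is a code-list edit and a re-run. There will be slightly fewer events in the ICD-9 period, and the cohort counts in sections 5c and 8 will change a little.

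### Allergic disease, prescription antihistamines and bladder antimuscarinics are not in the propensity score or the balance table, so their balance between arms is unknown

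*Combined protocol and SAP*

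**What the plan says.** Section 7 defines the score: "The PS will be calculated as the predicted probability of initiating the exposure of interest (i.e., the repurposing candidate) versus the reference drug". It fits the score "conditional on baseline covariates using multivariable logistic regression constructed separately in each data source" and presents matching on it as an "approach to account for measured confounding in this study". The score therefore directly targets only what Section 6b lists.

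Section 6b has a respiratory block, "Other Asthma treatments and Asthma severity indicators". It covers lung conditions, exacerbations, LABA, SABA, SAMA, LAMA, other inhaled steroids, biologics, other leukotriene antagonists and pulmonologist visits. Its only upper-airway entry is an infection: "Acute Upper/ Lower Respiratory Tract infection". The comedication block includes tricyclics, benzodiazepines, anti-epileptics, atypical antipsychotics and "Typical antipsychotics".

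Neither Section 6b nor the Section 8 table contains allergic rhinitis, another atopic diagnosis, antihistamines, bladder antimuscarinics or an anticholinergic-burden score. Asthma codes are pooled for cohort entry in Section 5b, and no asthma subtype is a covariate. The appendix is not described as adding variables: "ICD-9, ICD-10, HCPCS, and NDC codes used to define the covariates listed above are available in Appendix A".

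Section 9 plans no negative-control outcome, quantitative bias analysis or other check for unmeasured confounding.

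**The concern.** The plan already treats several sedating or anticholinergic drug classes as covariates for a dementia endpoint. It gives no reason for stopping short of antihistamines and bladder antimuscarinics, two further sources of anticholinergic exposure in patients aged 65 and over.

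If allergic disease also influences which of the two study drugs is started, antihistamine use could differ between arms after matching. If those drugs affect cognition, or the chance of a dementia work-up, part of the estimated hazard ratio would reflect them and not the study drugs. The Section 8 table cannot show this, because it reports only variables already in the list.

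**Working it through.** **1. Reproduce the plan's own balance figures.** The standardized difference for proportions is 100 × (p1 − p0) / √{[p1(1 − p1) + p0(1 − p0)] / 2}. For LABA after matching, p1 = 2532/12,572 = 0.2014 and p0 = 2143/12,572 = 0.1705, which gives 7.96 against the printed 8.00. Unmatched LABA is unreadable in the table; 2532/12,575 against 12,953/38,958 gives −29.98. Ten other binary rows were checked in both columns and LAMA, SAMA, tricyclics, antipsychotics and other inhaled steroids were among them; all agree with the printed values to rounding.

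**2. What the table shows for listed drugs with anticholinergic action** (montelukast minus fluticasone, printed values):

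| Class | Unmatched | Matched |
|---|---|---|
| Tricyclics | −2.80 | 0.40 |
| Atypical antipsychotics | −3.90 | 0.80 |
| Typical antipsychotics | −2.40 | −0.80 |
| LAMA | −5.50 | 0.00 |
| SAMA | −1.80 | 1.00 |

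All are within 1.0 after matching. Before matching all are slightly less common with montelukast. For the omitted variables the documents give no counts, so no standardized difference can be computed.

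**3. Possible size.** For one binary omitted confounder, the bias factor on the risk ratio is [1 + p1(RR − 1)] / [1 + p0(RR − 1)]. Here p1 and p0 are the prevalences in the montelukast and fluticasone arms, and RR is the confounder's relative effect on dementia. Applying it to a hazard ratio is an approximation that is reasonable when the outcome is uncommon; the documents give no event count. All prevalences and relative effects below are assumptions.

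| p1 vs p0 | RR | Factor | Factor with arms swapped |
|---|---|---|---|
| 10% vs 8% | 1.2 | 1.020/1.016 = 1.004 | 0.996 |
| 20% vs 14% | 1.3 | 1.060/1.042 = 1.017 | 0.983 |
| 30% vs 18% | 1.5 | 1.150/1.090 = 1.055 | 0.948 |

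For bladder antimuscarinics at 7% vs 5%, RR 1.2 gives 1.014/1.010 = 1.004 and RR 2.0 gives 1.07/1.05 = 1.019.

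**4. Are the assumed gaps plausible?** An omitted variable is best compared with the unmatched column, since the score does not target it. By the formula in step 1 the three scenarios have standardized differences of:

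- 0.02/√[(0.0900 + 0.0736)/2] = 7.0%
- 0.06/√[(0.1600 + 0.1204)/2] = 16.0%
- 0.12/√[(0.2100 + 0.1476)/2] = 28.4%

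In absolute size these are close to unmatched gender (7.00), other inhaled steroids (17.40) and LABA (29.98). The third scenario therefore assumes an imbalance near that of LABA, the widest percentage gap among the binary rows. More extreme inputs give more: 50% vs 30% at RR 2.0 gives 1.50/1.30 = 1.15, but nothing in the documents points to a gap of that size.

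**The case against.** A reader might infer that the matched arms remain unbalanced on allergic disease and antihistamines, and that the estimate is therefore biased against montelukast. The documents do not support that, for four reasons.

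- No counts are given, and matching on correlates can balance an unlisted variable in part. Candidates are in the list and closely matched: biologics (1.20), acute respiratory infection (−1.00), pulmonologist visits (0.90), outpatient visits (0.90).
- Nothing in the documents says that allergic disease drives the choice of montelukast. It is a clinical assumption.
- The direction is open. The fluticasone route is not stated. If nasal products count, allergic rhinitis could be as common or more common in the comparator arm, and the factor would fall below 1. The unmatched figures for listed anticholinergic classes do not point to heavier use with montelukast either.
- Bladder antimuscarinics are not given for allergy, so the allergic indication does not link them to treatment choice.

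It can also be said that Section 7 claims control of measured confounding only, and that adding strong predictors of treatment with little relation to the outcome can widen intervals, reduce overlap or amplify residual bias. An anticholinergic-burden score would overlap with classes already balanced.

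These points remove any claim of demonstrated imbalance or known direction, and they favour a sensitivity analysis over simply replacing the current score. They do not remove the omission, and the plan has no other check that would reveal its effect.

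**Conclusion.** The concern holds in a limited form. Allergic rhinitis or atopy, prescription antihistamines and bladder antimuscarinics are absent from the covariate list and from the balance table. They are not directly adjusted for, and their balance is unknown.

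The probable effect is small: a factor of about 1.004 to 1.06 on the assumed inputs, about 0.996 to 0.95 if the imbalance is reversed, and about 2% or less for bladder antimuscarinics, which matter only for completeness of anticholinergic exposure. These sizes rest on assumed prevalences and relative effects, and on allergic disease being related to treatment choice. This is an inexpensive improvement that should be made; the omission does not by itself invalidate the comparison.

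**What to change.** - In Section 5b or 6a, state which fluticasone formulations count as the comparator exposure.
- Add to Section 6b, and report by arm in Section 8 before and after matching: allergic rhinitis and other atopic disease, prescription sedating antihistamines, and bladder antimuscarinics.
- Re-estimate the score with these variables and rematch, at least as a sensitivity analysis beside the current score, and report the change in the hazard ratio.

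**Cost.** Section 5b already requires Parts A, B and D enrollment, so the diagnoses and prescriptions should be obtainable. The work is extra code lists and one rerun. The current score matched 12,572 of 12,575 montelukast starters from 38,958 fluticasone starters, so there is room for more covariates. If allergic disease strongly predicts treatment, however, a few matches may be lost or intervals may widen slightly. Over-the-counter antihistamines would still be unmeasured, with the allergic diagnosis as an imperfect proxy.
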